8.0 STATISTICAL CONSIDERATIONS

Analyses will assess the effectiveness between the three groups longitudinally on the primary and secondary outcomes.

Descriptive analyses. The research team will use descriptive statistics for all demographic and clinical variables across all three arms. To assess the impact of chance baseline imbalances between arms on intervention effect estimates, variables with noticeable differences will be included as covariates in a sensitivity analysis.

Intervention analyses. The analysis assesses direct treatment effects on patient outcomes over time over the 12-month study period. The research team will construct a longitudinal model of our outcome measures at 0, 1, 2, 3, 4, 5, 6, 7, 8, 9, 10, 11, and 12 months after randomization. The stratification variables will be by clinic, biological sex, and alcohol severity. They will be included as factors in the model and the baseline values of patient outcomes will be included as covariates, with a separate model for each primary outcome (risky drinking patterns, quality of life, and cost). This longitudinal analysis is complicated by the dependence among successive observations made on the same individual. Since complete control of measurement is not possible, there may be incomplete data from individual subjects. Therefore we will conduct a mixed-model analysis of repeated measures based on the general linear model with assessment of various covariance structures (compound symmetric, autoregressive order one, and unstructured). Covariance structure selection will be based on Akaike's information criterion and Schwarz's Bayesian criterion.^{46, 47} Pairwise comparisons between treatment groups and specific treatment time contrasts in the mixed model will be conducted to respond to between-group effects and time-based effects. To address issues of incomplete data we plan to estimate treatment effects according to 4 approaches: intention-to-treat, as-treated, per-protocol, and complier-average causal effect. Missing data patterns will be established from the longitudinal data and will be used to adjust the longitudinal intervention analysis according to pattern-mixture modeling.⁶⁹

Mediation analysis. To augment the intervention analysis, we will estimate the effects that mediating variables have on the outcomes. Services in Tula were developed to meet three psychological needs (competence, relatedness, and autonomous motivation) and accordingly the research team will use a mediational model in which patients in the clinically integrated Tula group will improve these psychological needs, relative to the peer-supported Tula group and the self-monitoring group. In turn, the research team will analyze whether improvements in the psychological needs correlates to improved patient outcomes. Analyses will control for baseline scores on outcome variables and the design variables that are used to stratify our sample during randomization (site). The research team will use structural equation models to assess both direct and indirect influences of our intervention on patient outcomes.⁷⁰ To test the mediation effects via the 3 psychological needs, a mediation model

Protocol

HS IRB #2019-0337
Version 5. 10/17/19
Version 6. 04/07/20
Version 7. 10/09/20
Version 8. 01/26/21
Version 9. 08/18/21
Version 10. 07/13/23

will be constructed to test the mediation effects between randomization variable and 12-month patient outcomes.

Operational cost analysis. Costs will be calculated based on tenets of engineering economics. This study will use incremental cost effectiveness ratios (ICERs) to quantify the tradeoff between the additional effectiveness achieved through clinical integration of the clinically integrated group compared to the peer-supported group. The main ICER will be the incremental cost per reduced drinking days over the 12-month period. We will train the health coach in the clinically integrated group to simulate use of CMS billing codes for mHealth to estimate potential reimbursement potential of the system that may be used to offset the costs of implementation.

Power. Power calculations are based on the previous randomized clinical trial of the platform.⁷¹ The study is powered to detect a difference between groups in risky drinking episodes across the 12-month intervention period. Based on the attrition rate in the previous randomized clinical trial of Tula, we assume an attrition rate of 23% over the course of the study. To detect an effect size of Cohen's $d=0.23$ the research team will recruit 182 patients per group (546 patients total) to have sufficient power ($1-\beta=0.8$, multiple comparison adjusted $\alpha=0.0167$, two-tailed). This would be a difference of 1.37 risky drinking episodes per month.

Quantitative data collection. The data collected in will come from multiple sources (see Table 1). Data collected from patient surveys will be collected by the Tula system and securely stored on CHESS servers. All log files will be stored on the CHESS server to be used to assess Tula use.

Qualitative data collection. This project will make use of clinician interviews to better understand the effect of Tula in the primary care setting. The interview will occur at intervention month 36 and take place at the clinicians' primary care clinic. Qualitative researchers will ask clinicians to talk about their experiences with Tula to refine the system for future use in primary care.

Qualitative data analysis. Content analysis will describe how Tula use can improve patient outcomes; identify potential improvements in Tula; and identify how qualitative data can supplement the quantitative analysis. A qualitative researcher will construct a coding scheme to assess the ideas of the study in order to capture references to a concept. The analyses will help the research team refine Tula for future dissemination by determining the individual and organizational conditions necessary to promote effectiveness.

Protocol

HS IRB #2019-0337
Version 5. 10/17/19
Version 6. 04/07/20
Version 7. 10/09/20
Version 8. 01/26/21
Version 9. 08/18/21
Version 10. 07/13/23

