Patient and clinician decision making	Value and decision framing survey	Patient/ clinician survey	9	Patient: Pretest, 12 months Clinician: during interview at month 36
Mediators				
Relatedness	CHESS Bonding Scale ^{48,65}	Patient survey	5	
Competence	Perceived Competence Scale	Patient survey	4	0, 3, 6, 9, 12 mo.
Autonomous motivation	TSRQ ⁶⁶	Patient survey	6	
Tula use (patients)	Number of days used, number of pages viewed	Server log files	NA	Continuous
Moderators				
Patient characteristics	Race, ethnicity, gender, age	Patient survey	NA	Pretest

Protocol

HS IRB #2019-0337
Version 5. 10/17/19
Version 6. 04/07/20
Version 7. 10/09/20
Version 8. 01/26/21
Version 9. 08/18/21
Version 10. 07/13/23

All survey data collected through Tula is housed on CHESS servers then exported to the UW sponsored Google Drive folder for statistical analyses.

Screening survey: People interested in participating in the study will be directed to take a Qualtrics screening survey hosted on the Web to determine if they are eligible to participate in the study.

Baseline survey. After patient subjects are enrolled in the study, they will be asked to take a baseline survey consisting of demographic questions, medical service utilization, quality of life, a modified version of the Brief Alcohol Monitor, the CHESS bonding scale, the alcohol competence scale, the TSRQ, and the value of Tula. Data from the screening survey will be used as baseline data for the AUDIT, AUD DSM-5, and timeline follow-back. Two additional questions related to the impact of COVID-19 on participants' physical and mental health will be added to the quality of life measures. These questions will operate on a 5-point Likert scale and will be included across all CHESS studies. (See supporting document "4.6.20 Global Health Scale v1.3_COVID.docx").

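### Extra covariates are chosen by observed imbalance and used only in a sensitivity analysis; the drinking model could prespecify the screening AUDIT score and DSM-5 count for a small gain in precision

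*Combined protocol and SAP*

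**What the plan says.** Three places bear on this.

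- **Section 8.0, Descriptive analyses.** To examine the effect of chance baseline imbalance on the effect estimates, "variables with noticeable differences will be included as covariates in a sensitivity analysis". The section does not say what counts as noticeable, which variables are candidates, or who decides.
- **Section 8.0, Intervention analyses.** Randomisation is stratified on alcohol severity, sex and clinic, and the plan says of these three variables: "They will be included as factors in the model and the baseline values of patient outcomes will be included as covariates". There is a separate model for each primary outcome (risky drinking, quality of life, cost).
- **Section 5.0, Baseline survey.** "Data from the screening survey will be used as baseline data for the AUDIT, AUD DSM-5, and timeline follow-back".

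Section 8.0 never names the AUDIT score or the DSM-5 count as a covariate. Sections 4.0, 7.0 and 8.0 all name alcohol severity as a stratification variable, but none states its instrument or cut-points. Section 6.0 lists the AUD scale, AUDIT and 7-day timeline follow-back under alcohol use disorder severity. Section 3.0 excludes patients with at least 6 of 11 DSM-5 symptoms, so the count among enrolled patients runs from 0 to 5.

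**The concern.** In a randomised trial a difference between arms at baseline is a chance event. Adjustment improves the estimate to the extent that the covariate predicts the outcome. A variable that differs visibly but predicts nothing adds nothing. A strong predictor that happens to be balanced would be left out, although adjusting for it would shrink the residual variance. Because the choice follows a look at arm-level data with no stated criterion, two analysts could also build different sensitivity models from the same data.

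The plan already holds two plausible predictors of drinking. The drinking baseline is a single 7-day report, while the difference used for power is in episodes per month (Section 8.0, Power), so one week may be a noisy baseline. A more stable severity score could add to it. At stake is some precision in the drinking comparison that needs no new data, and a sensitivity analysis that can be reproduced.

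**Working it through.** **Inputs from the documents (Section 8.0, Power).** Effect size d = 0.23; power 0.80; "multiple comparison adjusted $\alpha=0.0167$, two-tailed"; 182 per group, 546 in total; attrition 23%.

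**The plan's own figure.** With z(α) = 2.393 and z(β) = 0.842, the single-endpoint formula is n = 2[(z(α)+z(β))/d]² = 2(3.235/0.23)² ≈ 396 per arm, or 396/0.77 ≈ 515 after attrition. This does not reproduce 182. A repeated-measures mean under compound symmetry can do so, but only with a correlation that the plan does not state. With 13 assessments and correlation 0.30, the variance factor is (1 + 12×0.30)/13 = 0.354, giving 140 per arm and 140/0.77 ≈ 182. The figure is therefore under-documented rather than shown to be wrong. The stated 80% is taken as the starting point below.

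**Effect of an added covariate.** If it explains a share R² of the variance left by the planned model, the SE is multiplied by √(1−R²). Then:

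- power = Φ[(z(α)+z(β))/√(1−R²) − z(α)]
- patients saved, in equivalent terms = 546 × R²/(1−R²)

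| Partial R² | SE factor | Power | Equivalent patients |
|---|---|---|---|
| 0.00 | 1.000 | 80.0% | 0 |
| 0.01 | 0.995 | 80.5% | 5 |
| 0.02 | 0.990 | 80.9% | 11 |
| 0.05 | 0.975 | 82.3% | 29 |
| 0.06 | 0.970 | 82.7% | 35 |
| 0.14 | 0.927 | 86.3% | 89 |

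**Which R² is plausible.** The documents give no correlations, so these are assumptions: baseline with outcome (b) 0.5–0.7, AUDIT with outcome (a) 0.3–0.5, AUDIT with baseline (c) 0.4–0.6, joint normality. Only one continuous score is modelled; the DSM-5 count is not modelled separately.

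*Severity stratum not based on the score.* Partial R² = (a − bc)²/[(1−b²)(1−c²)]. The largest value on the grid is at b = 0.5, a = 0.5, c = 0.4: 0.30²/(0.75×0.84) = 0.143. The smallest is 0.

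*Severity stratum is a median split of the score, already in the model.* A median split correlates √(2/π) = 0.798 with its parent score, so it correlates 0.798×0.5 = 0.399 with the outcome and 0.798×0.4 = 0.319 with the baseline. At the same corner:

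- residual variance with baseline and split = 1 − (0.25 + 0.159 − 2×0.5×0.399×0.319)/(1 − 0.102) = 0.686
- residual variance with baseline and continuous score = 1 − (0.25 + 0.25 − 2×0.5×0.5×0.4)/(1 − 0.16) = 0.643
- partial R² = 1 − 0.643/0.686 ≈ 0.06

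Elsewhere on the grid the value falls to 0. At b = 0.6, a = 0.4, c = 0.5, for example, it is 0.009, giving power of about 80.4%.

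**The case against.** The strongest reply is that the primary analysis is already prespecified and adjusted. Severity and the baseline outcome are the two obvious predictors of later drinking, and both are in. The imbalance rule is a stated robustness check and makes no claim to precision. That stands, and it limits the point to an improvement rather than an error.

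A reader might infer more in four ways. The documents do not support any of them.

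- **That the primary result is biased or its error rate affected.** The rule operates only in a sensitivity analysis and does not change the primary model or test.
- **That the sensitivity test fails to hold its level.** With an assumed p<0.10 trigger (the plan gives none), simulated size is about 0.014–0.016 against 0.0167. That errs on the conservative side, in an analysis that is not confirmatory.
- **That the loss is large.** Partial correlations of 0.3 and 0.4 would be worth 546×0.09/0.91 = 54 and 546×0.16/0.84 = 104 patients. They require partial R² of 0.09 and 0.16 beyond severity and baseline, against 0.00–0.06 above. Even without overlap with the stratum, the assumed grid stops at about 0.14. The truncation of the DSM-5 count to 0–5 further weakens it as a predictor.
- **That the scores, and age, belong in every primary model.** Nothing in the documents shows that they predict quality of life or cost, or that age predicts any of the outcomes.

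One part of the reply does not stand. It assumes that the severity stratum already carries AUDIT or DSM-5 information. Section 6.0 makes this likely, but the plan does not say so.

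**Conclusion.** The point holds as a minor one. The selection rule uses the wrong criterion and has no definition, and two already collected severity scores are not used as scores in the drinking model. The primary estimate is valid as planned.

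The gain from using them is 0 to about 3 percentage points of power (80% to about 80–83%), or 0 to about 35 patients. It would rise to about 86% at most if the severity stratum uses neither AUDIT nor DSM-5. All of this rests on the assumed correlations, on taking the plan's 80% as given, and on near-complete screening scores. Completeness is a fair inference from their use in eligibility, but it is not stated. The direction does not depend on the exact values: a fixed, prognosis-based list is at least as good as an imbalance trigger, and it is reproducible.

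**What to change.** In Section 8.0:

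1. For the risky-drinking primary mixed model only, prespecify the continuous screening AUDIT score and DSM-5 symptom count as covariates, alongside the stratification factors and the baseline outcome.
2. Report the same model without these two scores as the sensitivity analysis.
3. Replace the noticeable-differences rule with a fixed list of prognostic covariates, set before any comparative data are seen.

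Stating the instrument and cut-points behind the alcohol-severity factor in the same edit would show which of the two ranges applies.

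The cost is SAP wording and two degrees of freedom, against about 420 expected completers (546 × 0.77). No new data are needed.

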Quarterly follow-up surveys. Starting at month 3, patient subjects will be asked to take surveys once every 3 months. The study team will ask patient subjects to take the following surveys: 1) quality of life, 2) a modified version of the brief alcohol monitor, 3) timeline follow-back, 4) CHESS bonding scale, 5) alcohol competence scale, 6) TSRQ, 7) medical services utilization (6 months and 12 months only), 8) AUD severity (12 months only), 9) value of Tula (12 months only), 10) quality of life and 11) AUDIT. Two additional questions related to the impact of COVID-19 on participants' physical and mental health will be added to the quality of life measures. These questions will operate on a 5-point Likert scale and will be included across all CHESS studies. (See supporting document "4.6.20 Global Health Scale v1.3_COVID.docx").

Use data. The app automatically collects use data by placing "cookies" on subjects' smartphones (with patients' consent) when randomization takes place. Data are stored on a secure central server at CHESS.

Qualitative interviews. In order to better understanding the implementation of Tula in the health coaching and peer mentoring organizations, the study team will use the CFIR framework to interview the two health coaches and four peer mentors, as well decision makers in these organizations. In order to better understand the conditions under which Tula can be sustained, the team will conduct interviews with organizational decision makers and health system decision makers. Sample questions for each of these interviews are shown below. Interviews will take place at month 36 and last 30-60 minutes. Members of the research team who have received training in qualitative interviewing will conduct the interviews. Interviews will be conducted via a secure video conference call (Zoom) and will be audio recorded. Participant identities will be protected. Any identifiers will be coded in the transcripts so that there will be no way to link clinicians to their interview responses. Data collected will be used to refine the system for future dissemination.

Protocol

HS IRB #2019-0337

Version 5. 10/17/19

Version 6. 04/07/20

Version 7. 10/09/20

Version 8. 01/26/21

Version 9. 08/18/21

Version 10. 07/13/23

For health coaches and peer recovery workers	Sample Implementation Questions
CFIR Domain	

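### The primary longitudinal model uses the month-0 outcome both as a response and as the baseline covariate

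*Combined protocol and SAP*

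**What the plan says.** Section 8.0, Intervention analyses, specifies a "longitudinal model of our outcome measures at 0, 1, 2, 3, 4, 5, 6, 7, 8, 9, 10, 11, and 12 months after randomization". It then adds the stratification factors and states that "the baseline values of patient outcomes will be included as covariates, with a separate model for each primary outcome". The fit is a mixed model with "assessment of various covariance structures (compound symmetric, autoregressive order one, and unstructured" candidates, chosen by AIC and BIC. Effects are read from "Pairwise comparisons between treatment groups and specific treatment time contrasts in the mixed model"; none is named as primary.

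Section 5.0 shows where the month-0 values come from. For drinking: "Data from the screening survey will be used as baseline data for the AUDIT, AUD DSM-5, and timeline follow-back". Quality of life and utilization come from "a baseline survey consisting of demographic questions, medical service utilization, quality of life". Later surveys follow: "Starting at month 3, patient subjects will be asked to take surveys once every 3 months". Table 1 lists drinking and quality of life at months 0, 3, 6, 9 and 12.

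Nothing in the document takes month 0 out of the response, sets the arm means equal there, or drops the covariate. The Mediation analysis paragraph, by contrast, names 12-month outcomes as the response and baseline scores as controls.

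**The concern.** Month 0 precedes any treatment effect, and its value is the covariate itself. If it also enters as a response, the model is asked to predict a number from itself. Three things can then go wrong:

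- A group main effect is averaged over a visit where the effect is zero.
- The artificially small month-0 residuals are pooled into the variance and make post-baseline standard errors too small.
- An unstructured covariance can drive the month-0 residual to zero.

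This is the stated model for every primary outcome, and the plan leaves open the parameterisation that decides which of these occurs.

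**Working it through.** **Inputs.** Section 8.0, Power, gives d = 0.23, 182 per arm, 23% attrition, two-sided alpha 0.0167 (critical z 2.394) and a difference of 1.37 episodes per month. Completers: 182 × 0.77 = 140 per arm. Implied SD: 1.37/0.23 = 5.96. The within-patient correlation ρ is not given; 0.3 to 0.7 is assumed (between adjacent visits for AR(1)), with complete data and a constant post-baseline effect. Outcomes are scaled to unit variance. T is the number of times including month 0: 13 in section 8.0, 5 in Table 1. Let m = T − 1.

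**The plan's own figure.** A plain two-mean formula gives 2(2.394 + 0.842)²/0.23² = 396 per arm, or 396/0.77 = 515 after attrition, not 182. That is a separate matter and is not used as evidence here.

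**1. Main effect, compound symmetry.** The fit reduces to regressing each patient's mean over all T visits on arm and baseline. Month 0 contributes no arm difference, so the estimate is multiplied by m/T:
- 13 times: 12/13, so 1.37 becomes 1.26.
- 5 times: 4/5, so 1.37 becomes 1.10.

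The residual of that mean is m/T times the residual of the post-baseline mean. The standard error shrinks equally, and the test and its power are unchanged.

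**2. Treatment by visit, compound symmetry.** The common baseline slope is b = (1 + mρ)/T. Example with T = 5, ρ = 0.5: b = (1 + 2)/5 = 0.6.
- Residual variances: month 0, (1 − b)² = 0.16; later visits, 1 − 2bρ + b² = 0.76. Mean: (0.16 + 4 × 0.76)/5 = 0.64.
- Residual covariances: month 0 with later, (1 − b)(ρ − b) = −0.04; later pairs, ρ − 2bρ + b² = 0.26. Mean: (4 × (−0.04) + 6 × 0.26)/10 = 0.14.
- Model variance of the four-visit average: (0.64 + 3 × 0.14)/4 = 0.265.
- True variance: (1 + 3 × 0.5)/4 − 2 × 0.6 × 0.5 + 0.36 = 0.385.
- SE ratio: √(0.265/0.385) = 0.83. Actual type I error: 2[1 − Φ(2.394 × 0.83)] = 4.7%.

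For the average minus month 0, the model variance is (0.64 − 0.14)(1 + 1/4) = 0.625. The true variance is 0.625 + 1 − 2 × 0.5 = 0.625. That contrast has the correct SE.

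**3. AR(1).** Slope, variance and correlation were fitted numerically to the population covariance, and each model SE was compared with the true SE.

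| Result over ρ 0.3-0.7 | 13 times | 5 times |
|---|---|---|
| Main effect, CS: multiplier | 0.92 | 0.80 |
| Main effect, AR(1): multiplier | 0.82-0.90 | 0.70-0.76 |
| As episodes per month | 1.12-1.23 | 0.95-1.05 |
| AR(1) size with month 0 | 0.7-1.1% | 0.7-0.8% |
| AR(1) size without month 0 | 1.2-1.6% | 1.4-1.6% |
| AR(1) power with vs without, ρ 0.3 | 99.4 vs 99.6% | 68.0 vs 77.5% |
| ρ 0.5 | 94.1 vs 96.6% | 54.4 vs 68.1% |
| ρ 0.7 | 74.8 vs 86.3% | 48.4 vs 66.2% |
| By visit, CS: type I error, post-baseline average | 2.7% | 4.6-4.8% |
| By visit, CS: month 12 | 1.9-2.1% | 2.6-3.0% |
| By visit, AR(1): average | 2.1-2.2% | 3.3-3.6% |
| By visit, AR(1): month 12 | 1.8-2.8% | 2.8-5.5% |
| By visit, AR(1): first post-baseline visit | 0.5-1.4% | 0.6-1.6% |

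Under compound symmetry, the chance that any of the three pairwise tests on the average rejects falsely is 6.3-6.8% (13 times) and 11.7-12.1% (5 times). For the month-12 change contrast, whose SE is correct, it is 3.9-4.6%. Simulation (three arms of 140, 6,000 trials per setting) agreed closely; for example, AR(1) main-effect power at ρ 0.7 was 75.2 vs 86.5% (13 times) and 48.2 vs 66.0% (5 times).

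**4. Unstructured.** Residual differences from month 0 contain neither b nor the time-constant treatment and stratum terms. Multiplying (1 − b) and the other month-0 terms by s therefore changes the ML log-likelihood by −N log s, which grows without limit as s approaches 0 (b approaches 1). In one simulated data set with N = 280, the log-likelihood rose from −429.1 at b = 0.99 to 215.6 at b = 0.999. The rise of 644.7 equals 280 × ln 10. Without month 0 the same data gave −1348.3 at b = 0.5, falling to −1416.3 at b = 0.999999.

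Iterated ML (2,000 trials in each of 12 settings, true d 0 or 0.23) gave:
- Main-effect model: absolute estimate below 0.00004 in all 24,000 trials.
- Treatment-by-visit model: unbiased, but reduced to change-score contrasts. Power at ρ 0.3/0.5/0.7 was 43/57/84% against 91/88/94% for a baseline-adjusted analysis (13 times), and 37/51/78% against 76/77/89% (5 times).

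**Cost outcome.** Utilization is surveyed at baseline and then "medical services utilization (6 months and 12 months only", so a compound-symmetry main effect there would shrink by 2/3. This applies to that survey only. Section 6.0 also counts intervention and implementation costs, for which no month-0 value is described.

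**The case against.** The kindest reading is that month 0 is listed only as a measurement time and that a conventional analyst would use it as the covariate alone. The authors may have meant that. But the sentence defines the model's content, and an analyst who follows it will include month-0 rows.

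For drinking, a second pre-randomisation measure exists, because the first weekly survey is completed during run-in (section 5.0). If that were the month-0 response, the two numbers would differ. However, Table 1 names the follow-back as the drinking measure and section 5.0 names its screening value as baseline. A run-in value would also precede treatment and still dilute a main effect.

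Several limits do stand:
- No primary contrast is named, so the consequences are alternatives and do not occur together. The inflated error rates need a contrast that keeps month 0 in the response but leaves it out of the average.
- On the 13 written times under compound symmetry the effect is modest: 1.26 for 1.37 with the test unchanged, or 2.7% against 1.67%.
- The larger figures belong to Table 1's five times. The AR(1) columns apply the same adjacent-visit correlation to one-month and three-month spacing, so they describe different processes.
- The calculations assume complete data, while the plan expects 23% attrition.
- Software may report non-convergence for the unstructured fit, which would expose the problem. The plan would then have no valid rule for comparing its three structures.

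**Conclusion.** The concern holds: the model as written is wrong, and more than a missing detail. Under each of the three listed covariance structures at least one of the contrasts the plan allows is distorted.

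- **Main effect:** too small under compound symmetry and AR(1), with real power loss under AR(1).
- **Treatment by visit:** type I error of the post-baseline average up to 4.8% against a nominal 1.67%.
- **Unstructured:** no maximum, so AIC and BIC cannot choose.

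Some results are unaffected: the compound-symmetry main-effect test, change-from-month-0 contrasts under compound symmetry, and the first post-baseline visit under AR(1), which is not inflated. The sizes rest on the assumed correlations, complete data and a constant effect. The double use of month 0 and the unbounded likelihood do not depend on the assumed correlation.

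**What to change.** In section 8.0, Intervention analyses, choose one of two standard forms:

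1. Restrict the response to post-baseline visits and keep the baseline value as a covariate.
2. Keep month 0 as a response, constrain the arm means to be equal there, and drop the baseline covariate.

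In either case, state that the treatment contrast is taken over post-baseline visits only. With form 1 (four follow-ups, compound symmetry, ρ 0.5, 140 per arm) the estimate targets 0.23 with SE √(2 × 0.375/140) = 0.073. Here 0.375 is the adjusted variance 0.625 − 0.25. The 1.67% level is kept and power is about 77%.

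The cost is one or two sentences, with no new data and no change to the sample size. Covariance structure and any baseline-by-visit terms remain the sponsor's choice. Reconciling the 13 listed times with Table 1 is a separate correction.
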